## 1. Study Design

**Study Type:** Prospective single-central observational study

**Observational Study Model:** Case-Only

**Study Start:** February 18, 2024

**Estimated completion date:** October 1, 2024

## 2. Methods for generating random sequence assignments

N/A.

## 3. Blindness and blinding

N/A.

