2. The study aims to explore the correlation between albumin, adenosine deaminase (ADA), lymphocyte-monocyte ratio (LMR), prognostic nutritional index (PNI) and other inflammation indicators in drainage fluids on day 1 and day 3 following colorectal cancer surgery, and the occurrence of POGD.

3. The study aims to explore the correlation between neutrophil-lymphocyte ratio (NLR), lymphocyte-monocyte ratio (LMR), platelet-lymphocyte ratio (PLR), systemic immune-inflammatory index (SII), and other inflammation indicators in peripheral blood on day 1 and day 3 following colorectal cancer surgery, and the occurrence of POGD.

4. Combined inflammatory markers in peritoneal fluid and peripheral blood to predict POGD.

5. To evaluate the practical application of the I-FEED score in clinical practice.

3. Study endpoints

Primary endpoint:

Grading of postoperative gastrointestinal function (according to the scoring system based on intake, sensation of nausea, vomiting, physical examination, and duration of symptoms (I-FEED). normal (0-2), postoperative gastrointestinal intolerance (POGI) (3-5), and postoperative gastrointestinal dysfunction (POGD) (>6).

Secondary endpoints:

- a. Time to first postoperative deflation.
- b. Time to first postoperative bowel movement.
- c. Time to first postoperative food tolerance.
- d. Morbidity and mortality from 30-day postoperative complications .

4. Outcome Measures

Primary Outcome Measure:

Measurement of drainage fluid lactate dehydrogenase (LDH) and neutrophil to lymphocyte ratio (NLR) on postoperative day 1

Secondary Outcome Measure :

- a. Measurement of drainage fluid LDH and neutrophil to lymphocyte ratio (NLR) on postoperative day 3.
- b. Measurement of drainage fluid albumin, adenosine deaminase (ADA), lymphocyte-monocyte ratio (LMR), prognostic nutritional index (PNI) on postoperative day 1.
- c. Measurement of drainage fluid albumin, adenosine deaminase (ADA), lymphocyte-monocyte ratio (LMR), prognostic nutritional index (PNI) on postoperative day 3
- d. Measurement of blood serum neutrophil-lymphocyte ratio (NLR), lymphocyte-monocyte ratio (LMR), platelet-lymphocyte ratio (PLR), systemic immune-inflammatory index (SII) on postoperative day 1.
- e. Measurement of blood serum neutrophil-lymphocyte ratio (NLR), lymphocyte-monocyte ratio (LMR), platelet-lymphocyte ratio (PLR), systemic immune-inflammatory index (SII) on postoperative day 3.

4.Sample collection

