Patient drainage fluid was collected on the first and third postoperative days. All samples were transferred to the laboratory for analysis within 30 minutes, and collected samples were aliquoted into 2 ml cryotubes and stored at -80 degrees Celsius until further use. Cytological analyses for neutrophils, lymphocytes, monocytes, etc. were performed using a Sysmex XN 1500 (Sysmex, Shanghai). Biochemical assays were performed using an AU480 chemistry analyzer (Beckman Coulter, USA) with enzyme kinetic assay for lactate dehydrogenase, peroxidase assay for adenosine deaminase and bromocresol green assay for albumin.

5.Follow-up plan

Content	Cytology (drainage fluid)	Biochemical (drainage fluid)	Biochemistry (peripheral blood)	Cytology (peripheral blood)	Consultation	medical examination	pathological results
preoperative			√	√			√
POD.1	√	√		√	√	√	
POD.2					√	√	
POD.3	√	√		√	√	√	
POD.4					√	√	
POD.5					√	√	
postoperative							√

POD: Post-operative day

6. Study Design

Study Type: Prospective single-central observational study

Observational Study Model: Case-Only

Study Start: February 18, 2024

Estimated completion date: October 1, 2024

7. Study population

7.1 Inclusion Criteria:

- Preoperative diagnosis of colorectal cancer through colonoscopy biopsy.
- Patients aged 18-80 years.
- Underwent laparoscopic radical resection for colorectal cancer with confirmed postoperative pathology.
- No prior radiotherapy, chemotherapy, or immunotherapy before surgery.
- Voluntary participation in the study and signing of a written informed consent form.

7.2 Exclusion Criteria:

- Pregnant or lactating women.
- Severe liver dysfunction (Child-Pugh class B or above); severe renal dysfunction

(serum creatinine level greater than 177).

- Patients with severe heart failure, chronic obstructive pulmonary disease, and other underlying diseases.
- Patients with pre-existing severe infections (developing sepsis or not improving after antibiotic treatment) before surgery.
- Patients with postoperative fistulas or those requiring a two-stage anastomosis.
- Intraoperative and postoperative intraperitoneal chemotherapy.
- Blood disorders (leukemia, lymphoma, aplastic anemia, etc.).
- Patient or family member withdraws midway;
- Intraoperative or postoperative instability of vital signs requires admission to the intensive care unit.
- Those with serious post-operative infections (e.g., incisional, lung, and urinary tract infections)

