## **5. Statistical analysis**

Statistical analyses were performed by SPSS statistical software v.17.0 (SPSS Inc., Chicago, IL, USA) and R Language v.4.0.3 (R Foundation for Statistical Computing, Vienna, Austria). Measures that met normality were expressed as mean  $\pm$  standard deviation were analyzed using the t-test, and measures that did not meet normality were expressed as median and interquartile range and analyzed using the Mann-Whitney rank sum test. The cutoff value was selected by the use of the Youden index (sensitivity + specificity - 1), and the count data were expressed as number of cases and percentages and analyzed using chi-square test. Predictors of postoperative complications and POGD were studied by univariate and multivariate logistic regression (LR). The diagnostic performance of biomarkers was assessed by receiver operator curve (ROC) analysis.

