## **6. Data collection and management**

Simultaneous recording of electronic data and paper report forms.

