## **7. Data Management Programmer**

Paper files were sealed one at a time in the order of entry into the group, opened and recorded during interim analysis and data analysis, and stored and backed up in a timely manner. Regularly updated on [clinicaltrials.gov](https://clinicaltrials.gov).

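### Blinding is entered as N/A, and nothing in the plan keeps I-FEED scorers unaware of the drain-fluid markers or controls when marker results are released

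*SAP*

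**What the plan says.** - **Blinding.** SAP section 3, "Blindness and blinding", is answered N/A, with no reason and no mention of outcome assessors or laboratory staff.
- **Outcome.** Protocol section 3 (Study endpoints) grades gastrointestinal function by a "scoring system based on intake, sensation of nausea, vomiting, physical examination, and duration of symptoms (I-FEED").
- **Marker.** The primary measure in the protocol's Outcome Measures section is "Measurement of drainage fluid lactate dehydrogenase (LDH) and neutrophil to lymphocyte ratio (NLR) on postoperative day 1".
- **Timing.** The follow-up table in protocol section 5 has drain fluid on days 1 and 3, and consultation and medical examination on each of days 1 to 5.
- **Sample handling.** The protocol's Sample collection section says "All samples were transferred to the laboratory for analysis within 30 minutes". The same sentence has aliquots "stored at -80 degrees Celsius until further use".
- **Records.** SAP section 6 has "Simultaneous recording of electronic data and paper report forms". SAP section 7 has paper files sealed in order of entry, then "opened and recorded during interim analysis and data analysis".
- **Analysis.** SAP section 5: "The diagnostic performance of biomarkers was assessed by receiver operator curve (ROC) analysis".

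The documents do not say who scores I-FEED, which day's score defines POGD, when laboratory results are reported and to whom, or what the sealed files hold.

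**The concern.** Without randomised treatment there is no allocation to conceal. A marker-accuracy study needs a different kind of blinding: the outcome should be graded without knowledge of the marker, and the marker measured without knowledge of the outcome. An ROC analysis takes the outcome grade as an independent reference. If the grader knows that a patient's drain-fluid LDH or NLR is high and expects POGD, part of the measured agreement is created by the grading.

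I-FEED leaves room for this. Reported nausea and the examination involve judgement, and the grades are bands of a short score, so a small shift can move a patient across a boundary. The expected direction is also known locally, because the pretest figures in SAP section 4 show higher LDH and NLR in POGD patients. The primary result is at stake, and nothing the plan collects would show afterwards which grades had been influenced.

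**Working it through.** **1. Can the marker be known when the outcome is scored?** The primary marker is sampled on day 1 and examinations run on days 1 to 5, so four of the five assessment days follow the sampling day. Transfer within 30 minutes makes same-day results possible. Freezing until further use makes later batch assay possible, at least for the biochemistry. The text fixes neither. Early knowledge of the result is therefore neither shown nor excluded.

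**2. Does any other text supply the masking?** The sealed paper files might, but their contents are not stated and electronic data are recorded in parallel. No other section bears on it.

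**3. Size of the bias if it occurs.** The plan states no figure to reproduce, so this is an illustration. Let A be the true AUC, p the POGD proportion and e the share of patients whose grade is set by whether the marker lies in its top fraction p. Patients whose true grade already agrees with the marker are unaffected, so e is also the share of discordant patients who are misrated. This rule leaves the POGD proportion at p. At fixed p, the AUC is a linear function of the mean marker rank among patients graded POGD, and a grade set entirely by the marker has AUC 1. Hence, in large samples,

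observed AUC = (1 − e)A + e = A + e(1 − A).

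Inputs: p = 3/8 = 0.375 (the 3:5 ratio in SAP section 4) and the pretest means and SDs in the same section. Under normality, A = Φ(difference / √(SD₁² + SD₂²)).

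- LDH: (1406.5 − 1210)/√(70² + 343²) = 196.5/350.1 = 0.561, so A ≈ 0.713.
- NLR: (156.3 − 39.4)/√(14.7² + 37.5²) = 116.9/40.3 = 2.90, so A ≈ 0.998.

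| Share e (assumed) | Useless marker, A = 0.50 | LDH, A = 0.713 | NLR, A = 0.998 |
|---|---|---|---|
| 5% | 0.525 | 0.727 | 0.998 |
| 10% | 0.55 | 0.741 | 0.998 |
| 20% | 0.60 | 0.770 | 0.999 |
| 30% | 0.65 | 0.799 | 0.999 |

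A simulation with 400,000 subjects agrees: 0.524, 0.549 and 0.599 for the useless marker, and 0.728, 0.743 and 0.771 for LDH, at 5%, 10% and 20%.

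**4. Effect on significance for a useless marker.** With 59 patients (the SAP's total before dropout) and a two-sided Mann-Whitney test at 0.05, simulation gives p < 0.05 in about 10%, 25% and just under 50% of studies at e = 10%, 20% and 30%. Few grades need to change. The expected number is 59 × e × 2 × 0.375 × 0.625, which is 2.8, 5.5 and 8.3 patients.

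**5. Direction.** Misrating unrelated to the marker lowers the AUC: 0.70 falls to about 0.66 when 10% of grades are flipped at random. Inflation needs rating that follows the marker in the expected direction.

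**The case against.** The strongest reply is that no passage shows a scorer seeing a result. The 30-minute figure is a transfer time, and the same sentence freezes the aliquots. A reader might infer that marker results are in hand before scoring. The documents do not support that, and this point does not claim it. The defect is that release is uncontrolled and masking is undescribed.

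A reader might also infer that N/A was entered because there is no randomisation. SAP section 3 gives no reason.

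The interim opening of the sealed files invites a further inference: that it unblinds scorers and should be deleted. That does not follow. The files are not said to hold marker results, and opening completed patients' files would not reveal the marker value of a patient still being scored. A rule protecting patients still being scored is enough.

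On size, the useless-marker case is the least favourable one. The plan's own pretest values imply a modest shift for LDH and almost none for NLR. The simulated scorer also applies a threshold that the plan does not supply at the bedside, since the cutoff comes afterwards from the Youden index. These limits stand, and the figures are conditional illustrations. Pretest values may themselves be optimistic, and normality is doubtful for an NLR with mean 39.4 and SD 37.5, so the smaller shifts are not assured either.

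None of this supplies the missing masking.

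**Conclusion.** The concern holds as a gap in the plan. Blinding is N/A, the outcome is partly subjective, most assessments follow the day 1 sample, and no text masks scorers or the laboratory or governs release of results. Upward bias in the primary ROC result therefore cannot be excluded; that it will occur is not shown.

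If it occurs, the AUC rises by e(1 − A). That is 0.05 to 0.15 for a useless marker at 10-30%, about 0.01 to 0.06 for LDH at its pretest values at 5-20%, and under 0.001 for NLR at its pretest values. These sizes rest on an assumed e, for which the documents give no basis, on normality for the pretest-based AUCs, and on influence running in the expected direction. The change is worth making because it is cheap and the bias could not be removed afterwards.

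**What to change.** Replace N/A in SAP section 3 with a rule covering these points:

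1. Name the role that scores I-FEED and the assessments that define POGD. Withhold research drain-fluid LDH, ADA, albumin and cell-count results from that scorer until the patient's last defining assessment is entered and locked.
2. Laboratory staff do not see I-FEED scores.
3. Any result released early for clinical need is logged with its date, and a sensitivity analysis excludes those patients.

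In SAP section 7, state what the sealed paper files contain, and that the file of a patient still being scored is not opened at an interim analysis. In SAP section 6, state who can see the parallel electronic record.

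The cost is a short SAP text, a laboratory release rule and an exception log. If the treating team scores I-FEED, early release unmasks the scorer for those patients, and the log and sensitivity analysis deal with that. Peripheral-blood counts used in routine care may stay visible to scorers and should be reported as a limitation of the blood-marker analyses. If masking is already practised, the change only writes it down.

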## 4. Sample size calculation

In a previously published study conducted at our institution, the incidence of postoperative prolonged ileal obstruction (PPOI) was approximately 38.0% (1), a figure we approximated to be equivalent to the incidence of postoperative gastric dysfunction (POGD). The ratio of the POGD group to the non-POGD group was approximately 3:5. Sample sizes were determined based on the primary study endpoints, and the mean lactate dehydrogenase (LDH) in the POGD group on postoperative day 1 (POD.1) was  $(1406.5 \pm 70)$ , as per the pretest results. The mean LDH for the non-POGD group was  $1210 \pm 343$ . Utilizing a one-sided, two-sample unequal-variance t-test with a power of 0.8 and an  $\alpha$ -value of 0.05, calculated using PASS2021 (NCSS, USA), the required number of cases was determined to be 45. The Neutrophil-to-Lymphocyte Ratio (NLR) value for the POD.1 POGD group was  $(156.3 \pm 14.7)$ , while the mean NLR value for the non-POGD group was  $(39.4 \pm 37.5)$ . The calculated sample size for this comparison was 8 cases, with a maximum sample size of 45 cases. In this study, age and TNM stage were primarily controlled as confounders. Assuming that 5 event samples are required to control for each variable, an additional sample of 14 cases is necessary,

bringing the total required sample size to 59 cases. Considering a 5% dropout rate, the final recruitment requirement is 63 cases.

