Title:

NCT number:

2024/1/08

Study Protocol

Title: Drainage Fluid Biomarkers and Postoperative Gastrointestinal Dysfunction in Laparoscopic Colorectal Surgery. A Monocentric Prospective Observational Study

NCT number: NA yet

Study data: 2024.01.08

1. Study background

Postoperative gastrointestinal dysfunction (POGD), often referred to as postoperative ileus (POI), is a common gastrointestinal issue that frequently occurs after colorectal surgery. It is characterized by symptoms such as nausea and vomiting, abdominal distension, and delayed defecation and evacuation. The incidence of POI is not clearly defined due to the varying definitions across healthcare institutions, but it is estimated to be approximately 10-30% and is one of the most common complications after colorectal surgery (1,2). The occurrence of POI increases the nutritional risk of patients (e.g., malnutrition, myasthenia gravis, malignant morbidity), prolongs the length of hospital stay, increases hospital costs, and significantly adds to the health economic burden (3,4).

In 2018, the American Society for Enhanced Recovery and Perioperative Quality Initiative Joint Consensus Statement considered abandoning the traditional definition of POI and proposed a scoring system based on intake, sensation of nausea, vomiting, physical examination, and duration of symptoms (I-FEED). They also introduced a definition of postoperative gastrointestinal dysfunction (POGD) based on scores classifying postoperative gastrointestinal function as normal (0-2), postoperative gastrointestinal intolerance (POGI) (3-5), and postoperative gastrointestinal dysfunction (POGD) (>6) (5).

The complex pathogenesis of POGD involves a brief neurogenic phase (within 3 hours) and a more prolonged inflammatory phase (beginning at 3-4 hours and lasting for days). The inflammatory phase is crucial and is recognized as initiated by mast cells and damage-associated molecular patterns that activate macrophages in the intestinal muscle layer. Subsequently, it triggers a series of cascading inflammation reactions through the release of inflammatory factors and recruitment of inflammatory cells, which contributes to the development and exacerbation of POGD.(6-13)

Levels of inflammatory cells and factors in the peritoneal fluid are changed following abdominal surgery in both rodents and humans (14,15). Many previous studies have confirmed that the use of drainage fluids also reduces the incidence of elevated inflammatory

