- Intraoperative conversion to open laparotomy.

8. Peri-operative procedures

The surgery was performed by an experienced surgeon (deputy head physician or above). The patient fasted for 6 hours and prohibited drinking water for 2 hours before the operation. General anesthesia was administered using static aspiration combined with endotracheal intubation under predominantly long-acting intravenous opioids (e.g. sufentanil). Anastomosis was performed using routine linear or circular techniques for resection of the left half of the colon, right half of the colon, sigmoid colon, and rectum, without the routine use of manual suture reinforcement. Drains were routinely placed in the post-operative period and removed after approximately 3 days post-operatively, once anastomotic fistulae and peritoneal effusion were excluded. Post-operative analgesia was provided. The patient utilized a patient-controlled intravenous paroxysmal pain regimen consisting of sufentanil (0.2ug/kg), tolstanesetron (5mg), and dizocin (20mg). Within 48 hours after surgery, the patient is allowed to consume fluids and enteral nutrition is gradually resumed as tolerated by the

patient. Patients were encouraged to mobilize early and were assisted in getting out of bed as they desired.

9. Ethics Statement

The study was conducted in accordance with the Declaration of Helsinki (as revised in 2013). The study was approved by the Ethics Committee of Chaoyang Central Hospital of China Medical University (2024 No. 02). Each subject was informed and signed an informed consent form prior to enrolment.

10. Reference

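### The 38% POGD rate is borrowed from PPOI and lies above the protocol's own 10-30%, so the adjusted models may have too few events by the SAP's 5-per-variable rule

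*SAP*

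**What the plan says.** SAP section 4 reports that, at the same institution, "the incidence of postoperative prolonged ileal obstruction (PPOI) was approximately 38.0" per cent, and calls this "a figure we approximated to be equivalent to the incidence of postoperative gastric dysfunction (POGD"). From it follows the planning split: "The ratio of the POGD group to the non-POGD group was approximately 3:5". The section sizes the LDH comparison at 45, adds 14 cases on a rule of 5 events per controlled variable (naming age and TNM stage), reaches 59, and recruits 63 to allow for 5% dropout.

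Protocol section 1 opens with "Postoperative gastrointestinal dysfunction (POGD), often referred to as postoperative ileus (POI"). It says the incidence is not clearly defined because definitions differ between institutions, and then that "it is estimated to be approximately 10-30% and is one of the most common complications after colorectal surgery".

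Under the I-FEED grading in protocol section 3, POGD is the top grade only, and scores of 3-5 form a separate grade (POGI). Protocol section 7.2 excludes, among others, "Intraoperative conversion to open laparotomy" and "Those with serious post-operative infections (e.g., incisional, lung, and urinary tract infections").

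SAP section 5 plans univariate and multivariate logistic regression for POGD, ROC analysis and Youden cutoffs. It does not list the model terms, give a range for incidence, or tie the model to the number of events observed.

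**The concern.** The planning rate is for a differently named outcome and lies above the top of the range the protocol gives for what it treats as the same condition. The SAP offers no data for the equivalence and no sensitivity range.

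Events limit everything here except the simple group comparison. If the true rate is inside the protocol's range, the adjusted odds ratios may rest on fewer events than the SAP itself requires. Sensitivity, which is estimated from POGD cases alone, would be imprecise. Because the terms are not fixed in advance, the number of variables could also be chosen after the event count is known.

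**Working it through.** **Inputs.** From SAP section 4: rate 38% (ratio 3:5); LDH 1406.5 (SD 70) with POGD and 1210 (SD 343) without; NLR 156.3 (SD 14.7) and 39.4 (SD 37.5); 5 events per variable; 59 evaluable. From protocol section 1: 10-30%.

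**The plan's own figures.**
- The 14 added cases: 5 / 0.38 = 13.2, rounded up to 14. They carry 14 × 0.38 = 5.3 events, enough for one variable, although two confounders are named. Two would need 10 / 0.38 = 26.3, so 27 cases.
- Recruitment: 59 / 0.95 = 62.1, so 63. This agrees.
- The 45: Welch t-test at 3:5, power from the noncentral t with Satterthwaite degrees of freedom. Groups of 17 and 28 give two-sided power 0.81, which matches 45. The one-sided test that the text describes ("Utilizing a one-sided, two-sample unequal-variance t-test with a power of 0.8") needs only 13 + 22 = 35. This mismatch is separate from the present point.

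**Expected events** = 59 × rate. Chance of reaching each threshold = upper tail of Binomial(59, rate).

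| Rate | Expected events | P(≥10) | P(≥15) | P(≥20) |
|---|---|---|---|---|
| 10% | 5.9 | 7% | 0.1% | <0.1% |
| 20% | 11.8 | 77% | 19% | 1% |
| 30% | 17.7 | 99% | 82% | 30% |
| 38% | 22.4 | >99% | 99% | 78% |

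**Events needed at 5 per variable**, and the rate at which 59 patients are expected to supply them:
- age + TNM (one term): 10 events; 10/59 = 16.9%
- one marker + age + TNM: 15 events; 15/59 = 25.4%
- LDH + NLR + age + TNM: 20 events; 20/59 = 33.9%

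TNM entered as a multi-level factor would need more.

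**LDH comparison.** One-sided Welch power at n = 59, difference 196.5, by group split:
- 6 + 53: 0.97
- 12 + 47: 0.97
- 18 + 41: 0.96
- 22 + 37: 0.95

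A lower rate does no harm because it moves patients into the group with the larger SD.

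**Sensitivity.** Illustrative exact (Clopper-Pearson) 95% intervals: 5 of 6 detected gives 36% to 99.6%; 18 of 22 gives 60% to 95%.

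**NLR near-separation.** If NLR were normal in both groups, AUC = Φ[(156.3 − 39.4) / √(14.7² + 37.5²)] = Φ(116.9 / 40.28) = Φ(2.90) = 0.998. Simulating 59 patients on these figures, every POGD value exceeded every non-POGD value in about 70% of samples at 22 + 37. With complete separation, maximum likelihood has no finite odds ratio. Normality is only an assumption: a ratio with mean 39.4 and SD 37.5 is probably skewed, and a long upper tail would make separation less frequent.

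**The case against.** The 38% is local data, openly labelled an approximation, whereas 10-30% is a loose literature range for ileus under varying definitions. Neither is an I-FEED POGD rate. That stands: the documents do not show that 38% is wrong, only that it is unsupported for this outcome and outside the protocol's range. The remedy is therefore a range that includes 38%, not a replacement rate.

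A reader might infer that the model fails at every rate from 10% to 30%. That is true only with LDH and NLR together beside age and TNM, and the SAP does not specify that model. The 5-event rule is written for the confounders. With one marker added, 30% gives 17.7 expected events against 15.

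A reader might also infer that the strict I-FEED grade and the exclusions must push the rate below 38%. This is plausible but not shown. The PPOI definition and the source study's eligibility are not in the documents, and 38% may already be net of similar exclusions.

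Finally, one could say that nothing is at stake because the sizing comparison is safe. That holds for the univariate LDH test. It does not cover the adjusted models or the ROC and Youden analyses, which serve the study's stated purpose of prediction.

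**Conclusion.** The concern holds as a conditional shortfall. At 38% the cohort supplies about 22 events, enough for one marker with age and TNM. Across the protocol's 10-30% it supplies 6 to 18. The one-marker adjusted model is then short, in expectation, below about 25%, and age plus TNM alone below about 17%. Only a joint LDH and NLR model would be short over the whole range.

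This rests on 59 evaluable patients, TNM as a single term, and the SAP's 5-per-variable rule taken at face value. It does not show that the trial is underpowered for LDH, or that the true rate is below 38%. The effect falls on the adjusted odds ratios, any combined-marker model, and the precision of sensitivity and cutoffs.

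**What to change.** In SAP section 4, state the expected number of events as a range, about 6 to 22 of 59, and say that 38% is a PPOI rate.

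In SAP section 5:
- Fit LDH and NLR in separate primary adjusted models, each always containing age and TNM, with TNM as one term. Do not drop a named confounder according to the observed event count, because the adjustment set would then depend on the data.
- Use Firth penalised logistic regression instead of plain maximum likelihood. It reduces small-sample bias and gives finite estimates under the near-separation that the SAP's NLR figures imply.
- Report sensitivity and specificity at the Youden cutoff with exact confidence intervals.
- Label any joint or combined-marker model exploratory when observed events are below 5 per term.

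The cost is SAP wording only, with no extra enrolment or procedures. Recruiting to an event count is the alternative, but 15 expected events would need 50 evaluable patients at 30%, 75 at 20% and 150 at 10%. The downside of the wording change is a less favourable stated event count, and the combined-marker model of secondary objective 4 may become exploratory. Firth regression also keeps an adjusted model estimable with few events, but it does not make the estimate precise.

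### The 45 cases in SAP section 4 do not follow from the one-sided test stated there: its LDH inputs give 35–36, and the same test run two-sided gives 45

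*SAP*

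**What the plan says.** SAP section 4 (Sample size calculation) assumes a POGD incidence of 38.0% and a POGD to non-POGD ratio of about 3:5. For day 1 LDH it takes 1406.5 (SD 70) with POGD and 1210 (SD 343) without. The calculation is described as "Utilizing a one-sided, two-sample unequal-variance t-test with a power of 0.8" at alpha 0.05, and "the required number of cases was determined to be 45". For NLR, "The calculated sample size for this comparison was 8 cases", so the LDH figure governs.

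The section then says that "age and TNM stage were primarily controlled as confounders" and continues: "Assuming that 5 event samples are required to control for each variable, an additional sample of 14 cases is necessary". The LDH figure and this addition are then summed, "bringing the total required sample size to 59 cases". After a 5% allowance for dropout, "the final recruitment requirement is 63 cases".

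SAP section 5 (Statistical analysis) says only that normally distributed measures "were analyzed using the t-test", with Mann-Whitney otherwise. It gives no sidedness, variance form or alpha.

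**The concern.** Section 4 supplies every input for the LDH calculation, so the 45 should be reproducible up to rounding of the group sizes. It is 9 to 10 cases too high for the test described, which is more than rounding explains.

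At stake is which error standard applies to one of the two primary markers. A one-sided test at 0.05 accepts some results that a two-sided test at 0.05 rejects. Because section 5 is silent on sidedness, the plan does not fix that choice anywhere except in a sentence whose number contradicts it.

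**Working it through.** **Inputs (all from SAP section 4).** Difference 1406.5 − 1210 = 196.5; SDs 70 (POGD) and 343 (non-POGD); ratio about 3:5; alpha 0.05; power 0.80; one-sided Welch test.

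**Formulas.** SE = √(70²/n₁ + 343²/n₂). Noncentrality = 196.5/SE. Degrees of freedom by Satterthwaite. Power = probability that a noncentral t exceeds the critical t.

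**The plan's figure, 17/28 = 45.** SE = √(288.2 + 4201.8) = 67.01; noncentrality 196.5/67.01 = 2.933; df 30.6.
- One-sided, critical t 1.696: power 0.889.
- Two-sided, critical t 2.041: power 0.810.

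**The smallest size for the test as stated (one-sided 0.05).**

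| POGD / non-POGD | Total | Power |
|---|---|---|
| 12/20 | 32 | 0.775 |
| 13/21 | 34 | 0.794 |
| 13/22 | 35 | 0.810 |
| 14/22 | 36 | 0.811 |
| 15/25 | 40 | 0.854 |

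The requirement is 35 or 36. If the groups must be exact multiples of 3 and 5, it is 40, because 12/20 falls short. The lowest total under any tolerable rounding is 34 (12/22, power 0.808).

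**The same inputs, two-sided 0.05.**

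| POGD / non-POGD | Total | Power |
|---|---|---|
| 16/27 | 43 | 0.795 |
| 17/27 | 44 | 0.796 |
| 16/28 | 44 | 0.809 |
| 17/28 | 45 | 0.810 |
| 17/29 | 46 | 0.824 |

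The result is 44 to 46, depending on how the ratio is entered and rounded.

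**Other single changes, kept one-sided.** Equal groups need 42 (21/21, power 0.801). Power 0.90 needs 47 (17/30, 0.907) or 48 (18/30, 0.908). Neither gives 45.

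**NLR.** For 156.3 (SD 14.7) against 39.4 (SD 37.5), 3/4 already has power 0.998 one-sided and 0.986 two-sided. The reported 8 is the smallest exact 3:5 split (3/5). It exceeds the target under either sidedness, so it cannot show which was used.

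**The step from 45 to 63.**
- Dropout: 59/0.95 = 62.1, rounded up to 63. This reproduces.
- The addition: 5 events at 38% need 5/0.38 = 13.2, so 14 cases. That covers one variable. Two variables need 10/0.38 = 26.3, so 27 cases.

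The totals therefore depend on two open points:

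| LDH base | Addition | Evaluable | Recruited (÷ 0.95) |
|---|---|---|---|
| 45 | 14 | 59 | 63 |
| 45 | 27 | 72 | 76 |
| 35–36 | 14 | 49–50 | 52–53 |
| 35–36 | 27 | 62–63 | 66–67 |

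**The case against.** Four points can be made for the plan.

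- **No harm to LDH.** The 45 exceeds what the stated test needs, so the comparison has more power than planned. This is correct and limits the severity. It does not make the statement consistent.
- **Another route reaches 45.** With the normal approximation, one-sided, power 0.90 and ratio 3:5, n₁ = (1.645 + 1.282)² × (70² + 343²/(5/3))/196.5² = 16.7 and n₂ = 27.9, that is 17/28. This changes both the method and the power, while section 4 names a t-test and power 0.8, so it is less likely than a two-sided entry. It does show that the two-sided reading is an inference, and why the software output must be checked.
- **The events may suffice anyway.** At 38%, 45 cases supply about 17 events and 59 about 22 (59 × 0.38 = 22.4). At 5 events per variable, 22 cover LDH, NLR, age and TNM stage if each is a single term (20 events). This stands: a shortfall under the plan's rule is not shown, and 76 should not be read as the required number. What is not shown is how 14 follows from two confounders.
- **Section 5 is a general paragraph.** It also assigns prediction to logistic regression and ROC analysis. True, and its silence alone would be only missing detail. It matters because section 4, the only place that states the sidedness, contradicts itself.

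**Conclusion.** The concern holds. The one-sided Welch test in section 4 needs 35–36 cases at power 0.80; the stated 45 gives it power 0.889. The same test two-sided gives 45 at power 0.810. This rests only on the section's own means, SDs, ratio, alpha and power; the single assumption is the rounding rule, which does not close the gap.

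The error is conservative for LDH. Its consequence is that the sizing statement cannot be reproduced and the sidedness of the test is unsettled. That two-sided was meant is likely but unproven. The figures of 59 and 63 are a separate matter and are not confirmed by settling the sidedness.

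**What to change.** 1. Check the sample size software output. If the entry was two-sided, change the sidedness in SAP section 4; the 45 then stands. If one-sided was intended, either restate the LDH requirement as 35–36 or keep 45 and give its power as about 0.89.
2. Check the 14 cases separately. Either show how they follow from 5 events for each of age and TNM stage, for example by counting the events already supplied by the base sample, or restate the addition and both totals.
3. Add to SAP section 5: *Day 1 LDH and NLR are compared between POGD and non-POGD patients with an unequal-variance (Welch) t-test at alpha 0.05, with the sidedness confirmed in section 4, or with the Mann-Whitney test at the same sidedness if normality is not met.*

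The cost is one look at the output and a few words of SAP text. If two-sided is confirmed, the 45 does not change; whether 59 and 63 change depends on step 2.
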